#### SPONSOR: GW PHARMA LIMITED

# 10 WITHDRAWAL

In accordance with the Declaration of Helsinki, the ICH Harmonised Guideline: Integrated Addendum to ICH E6(R1): Guideline for GCP E6(R2), the US FDA regulations relating to GCP and clinical trials, the EU Clinical Trials Directive, the EU GCP Directive, and/or other applicable regulations, a patient has the right to withdraw from the trial at any time and for any reason, with no obligation to provide a reason, and without prejudice to his or her future medical care by the physician or at the institution.

The patient must be withdrawn from the trial if any of the following apply:

- Administrative decision by the investigator, GW, or a regulatory authority
- Withdrawal of patient consent
- Lost to follow-up

The patient must cease IMP and should remain in the trial if any of the following apply:

- Pregnancy
- Protocol deviation that is considered to potentially compromise the safety of the patient
- Suicidal behavior, or suicidal ideation score of 4 or 5 during the treatment period, as evaluated with the C-SSRS
- ALT or AST  $> 3 \times$  ULN with the appearance of fatigue, nausea, vomiting, right upper quadrant pain or tenderness, fever, rash, and/or eosinophilia (> 5%)
- ALT or AST  $> 5 \times ULN$
- ALT or AST > 3 × ULN and (total bilirubin [TBL] > 2 × ULN or international normalized ratio [INR] > 1.5)
- Any prohibited medication after Visit 1

The patient may be required to cease IMP at the discretion of the investigator and should remain in the trial for any of the following reasons:

- Did not meet eligibility criteria
- Patient noncompliance
- AE (including clinically significant laboratory result) that, in the opinion of the investigator, would compromise the continued safe participation of the patient in the trial
- Any evidence of drug abuse or diversion

- Disease progression (defined as a relapse of MS requiring a change in treatment)
- A positive COVID-19 test result after randomization

Should a patient request or decide to withdraw consent from the trial, all efforts must be made to complete and report the observations as thoroughly as possible up to the date of withdrawal. Patients withdrawing due to an AE should be followed according to Section 12.7. All information should be reported on the applicable eCRF pages (refer to Section 9.2). A Safety Follow-up Visit should take place 14 ( $\pm$  4) days after the End of Treatment Visit (Visit 6) or Withdrawal Visit if the patient does not complete the remaining trial visits after discontinuing IMP (refer to Section 9.1.5). If withdrawing patients decline to give a reason for withdrawal of consent, the investigator must respect the patients' wishes.

Patients who withdraw from the trial will not be replaced.

## SPONSOR: GW PHARMA LIMITED

# 11 URGENT SAFETY MEASURES

During special circumstances (e.g., COVID-19 pandemic), the specific guidance from local public health and other competent authorities regarding the protection of individuals' welfare must be applied. In cases where participants are not able to perform all protocol-defined assessments due to special circumstances, the investigator must discuss with the medical monitor potential mitigation approaches.

For the duration of such special circumstances, the following measures may be implemented for enrolled patients:

- Safety follow-up may be done by a telephone call, other means of virtual contact or home visit, if appropriate.
- Patient and/or clinician-rated outcomes assessments may be done by videoconference, telephone call, other means of virtual contact, if possible.
- An alternative approach for IMP dispensing, secure delivery and collection may be sought.
- Visits may take place in a different location than defined in the protocol. If this is not feasible, then the visit may take place virtually with documentation of the means of communication (e.g., phone call or videoconference).
- Biological samples may be collected and analyzed at a different location than defined in the protocol. Biological samples should not be collected if they cannot be processed in a timely manner or appropriately stored until shipping/processing.
- If it is not possible to collect the biological samples or safety assessments (e.g., ECG, vital signs) within the interval predefined in the protocol (see the Schedule of Assessments in APPENDIX 1), then the interval may be extended up to a maximum duration of 3 days.
- If a safety assessment cannot be performed within the modified window, the investigator must review the benefit-risk for patient continuation in the study and record this in the medical records.

The rationale (e.g., the specific reasons behind the changes) and outcome of the discussion with the medical monitor will be documented in the medical record. Information on how each visit was performed will be recorded in the eCRF.

GW will report urgent safety measures to regulatory authorities and will provide a written report to the regulatory authorities and IRB/IEC within 3 days. Exceptional measures taken in response to COVID-19/other pandemic conditions and their impact on study results, such as tests done in a local laboratory, will be justified, assessed, and reported in the clinical study report in keeping with ICH E3.

#### SPONSOR: GW PHARMA LIMITED

The remote visit should include all protocol assessments that can be performed remotely (see minimum requirements, Table 11-1) and should take place within the original visit window, if possible. The investigator should make reasonable efforts to obtain these assessments which may include local clinicians, local laboratories and other resources. If these assessments cannot be obtained within a reasonable time outside the window of the scheduled visit date, the benefit-risk ratio for the patient to continue in the study should be reassessed.

The decision to replace a site visit with a remote visit will be made by the investigator, on a case-by-case basis, in consultation with GW, who should be informed of each visit to be rescheduled as early as possible.

If a telephone contact takes place at the time of stopping IMP, all safety data which can be obtained remotely should be collected as close as possible to the time of stopping IMP.
#### SPONSOR: GW PHARMA LIMITED

Table 11-1	Assessments R	equired at	t Minimu	m in the	Event of				
	Pandemic Con	-							
	Visit								
	2	3	4	5	6	7			
	Day 1	Day 15 14 days	Day 29 28 days from	Day 57 56 days from	End of Treatment /Early Withdraw al Day 85	Day 99 14 days from Visit 6			
	(Randomization)	from Day 1 (± 3 days)	Day 1 (± 3 days )	Day 1 (± 7 days )	84 days from Day 1 (± 7 days)	(± 4 days )			
C-SSRS	Х	Х	Х	Х	Х				
Review of concomitant medications	Х	Х	Х	Х	Х	Х			
Review of AEs	Х	Х	Х	Х	Х	Х			
MSSS-88	Х				Х				
MUS					Х				
Clinical laboratory blood sampling (hematology and biochemistry)	x		Х		Х				
Vital Signs	Х	Х	Х	Х	Х	Х			
12-lead ECG	Х		Х		Х				
Dipstick pregnancy test (if appropriate)	Х				Х				
eDiary completion	Х	Х	Х	Х	Х	Х			
IMP dosing training	Х								
IMP collection and compliance review		Х	Х	Х	Х				
IMP dispensing	Х	Х	Х	Х					

AE = adverse event; C-SSRS = Columbia-Suicide Severity Rating Scale; COVID-19 = coronavirus disease 2019; ECG = 12-lead electrocardiogram; IMP = investigational medicinal product; MSSS-88 = Multiple Sclerosis Spasticity Scale; MUS = Medication Use Survey

Notes:

- [1] During pandemic conditions only, sites may use local laboratories for safety assessments noted above, following consultation with the Sponsor.
- [2] Methodology for some assessments performed at locations other than the site (e.g., blood pressure cuff) will need to be pre-approved.
- [3] Under pandemic conditions, an initial IMP dosing training would be given at the site at Visit 1, with a refresher training given remotely at Visit 2. A training video would be supplied for IMP dosing training should pandemic conditions begin between Visits 1 and 2.
- [4] In cases where patients are not able to attend study visits due to COVID-19/other pandemic restrictions, the investigator will discuss with the Sponsor potential mitigation approaches for IMP dispensing and collection.
- [5] Data for the day of Visit 7 should not be entered in the electronic diary. Site staff will confirm that data that relates to the day prior to attending the site for Visit 7 has been entered in the electronic diary prior to completion of the trial.

#### SPONSOR: GW PHARMA LIMITED

# 12 ADVERSE EVENT REPORTING

#### 12.1 Definitions

# 12.1.1 Adverse Event

For the purposes of this trial, an AE is defined as follows:

Any new unfavorable/unintended signs/symptoms (including abnormal laboratory findings when relevant), or diagnosis or worsening of a pre-existing condition, that occurs following Screening (Visit 1) and at any point up to the post-treatment Safety Follow-up Visit (Visit 7), which may or may not be considered related to the IMP. Any event that is the result of a trial procedure must be recorded as an AE.

Surgical/investigational procedures are not AEs. The medical reason for the procedure is the AE. Elective hospitalizations for pre-trial existing conditions or elective procedures are not AEs. An exception may be if the patient has an AE during hospitalization that prolongs his/her scheduled hospital stay, in which case it would be considered an SAE (refer to Section 12.2).

If reporting a fatal event, the SAE term should be the underlying cause of the death (e.g., disease or medical condition leading to death).

#### 12.1.2 Investigator

The term investigator refers to the trial PI or a formally delegated trial physician.

# 12.2 Serious Adverse Events

During clinical investigations, AEs may occur that, if suspected to be IMP related, might be significant enough to lead to important changes in the way the IMP is developed (e.g., change in dose, population, monitoring need, consent forms). This is particularly true for events that threaten life or function. Such SAEs will be reported promptly to regulatory authorities, applicable IRBs/IECs, and investigators (expedited reporting) by GW.

An AE must only be classified as serious, i.e., an SAE, when the event falls into 1 of the following criteria:

- Results in death
- Is life-threatening\*
- Requires inpatient hospitalization or prolongation of existing hospitalization
- Results in persistent or significant disability/incapacity
- Is a congenital anomaly/birth defect
- Is medically significant\*\*

\*The term "life-threatening" in the definition of "serious" refers to an event in which the patient was at risk of death at the time of the event; it does not refer to an event that, hypothetically, might have caused death if it were more severe.

\*\*Medical and scientific judgment should be exercised in deciding whether SAE reporting is appropriate in other situations. Important medical events may not be immediately life-threatening or result in death or hospitalization but may jeopardize the patient or may require intervention to prevent one of the other outcomes listed in the definition above. These should also usually be considered serious. Examples of such events are intensive treatment in an emergency room or at home for allergic bronchospasm, blood dyscrasias or convulsions that do not result in hospitalization, or development of drug dependency or drug abuse. In addition, a positive test result for COVID-19 is to be recorded as an SAE.

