10.23.2 COVID-19 Adverse event

A confirmed or suspected COVID-19 adverse event will be any adverse event for which the AE term or the preferred term include the text "COVID-19" but should not be "COVID-19 ELISA test negative".

For instance, confirmed COVID-19 Treatment emergent adverse event (TEAE) will be reported as:

- COVID-19 infection
- COVID-19 disease
- COVID-19 pneumonia
- COVID-19 respiratory infection
- Asymptomatic COVID-19

whereas a suspected COVID-19 AE will be coded as Suspected COVID-19.

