12.8.1 Adverse Events

Adverse events will be coded using MedDRA 23.0 or higher according to the version in use at time of database lock. All safety analyses will be performed by actual treatment arm and reported using the SAF. A TEAE is one that started, or worsened in severity or seriousness, following the first dose of IMP. Any adverse event that worsens or becomes serious after the first IMP dose are recorded as a separate AE, therefore for programming purposes an AE will be classified as a TEAE if it first occurs on or after the IMP Start Date and before the IMP End Date + 30 days.

All AEs will be classified during the pre-treatment period, the 24-week on-treatment period or during the follow-up period as follows:

- Events that occurred before IMP Start Date are classified as pre-treatment AEs
- Events that occurred between IMP Start Date and 30 days after IMP End Date are considered on-treatment and classified as treatment-emergent AEs (TEAEs)
- Events occurring more than 30 days after IMP End Date are classified as follow-up AEs.

The following counting rules will be applied:

- For incidence reporting, if a patient reported more than one AE that was coded to the same preferred term/system organ class within a given treatment arm, the patient will be counted only once for that specific preferred term/system organ class by treatment arm and the rules defined below will be applied.
- For TEAEs presented by action taken on IMP, the worst action taken among the events with same SOC/PT will be selected for each patient. If action taken is missing for a TEAE, the action taken "drug withdrawn" will be assigned considering the AE leads to permanent IMP discontinuation. The imputed values for action taken will be used for incidence summaries, while the actual values will be used in data listings.
- For TEAEs presented by severity, the worst severity among the events with same SOC/PT will be selected for each patient. If the severity is missing for a TEAE, then a severity of "Severe" will be assigned. The imputed values for severity assessment will be used for incidence summaries, while the actual values will be used in data listings.

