12.8.2.2 Serious Adverse Events

Descriptive presentations of serious TEAEs will be given by PT and SOC for the SAF. The number and percentage of patients reporting at least one serious TEAE, as well as the number of events, within a given treatment arm will be provided as described below:

- All serious TEAEs by SOC and PT,
- All serious TEAEs by SOC, PT and subgroups (as described in Table 9.3-3),
- All serious TEAEs leading to permanent IMP discontinuation by SOC and PT,
- All serious treatment-related TEAEs by SOC and PT,
- All serious treatment-related TEAEs by SOC and PT leading to permanent IMP discontinuation by SOC and PT.

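### Every positive COVID-19 test counts as an SAE, and the SAP has no serious TEAE summary without COVID-19, so the aggregate serious TEAE rate is hard to interpret

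*Protocol*

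**What the plan says.** Protocol 12.2 opens with a restrictive rule: "An AE must only be classified as serious, i.e., an SAE, when the event falls into 1 of the following criteria". Six criteria follow, and the last is "Is medically significant". Its footnote begins: "Medical and scientific judgment should be exercised in deciding whether SAE reporting is appropriate in other situations". The final sentence of the same footnote is: "In addition, a positive test result for COVID-19 is to be recorded as an SAE".

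SAP 10.23.2 finds COVID-19 events by searching the reported term or preferred term for the name. Its examples of confirmed events include "Asymptomatic COVID-19".

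SAP 12.8.1 sets the window: "Events that occurred between IMP Start Date and 30 days after IMP End Date are considered on-treatment". SAP 12.8.2.2 then reports "The number and percentage of patients reporting at least one serious TEAE, as well as the number of events", with a table of "All serious TEAEs by SOC and PT". The overall summary in SAP 12.8.1.2 has a serious TEAE row and a separate row for confirmed or suspected COVID-19, but the two are not crossed. The addendum (Table 7-1) keeps SAP 12.8.1 and 12.8.2, and none of its exclusions removes the table of all serious TEAEs.

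**The concern.** A patient with an asymptomatic positive test and a patient admitted to hospital each add one to the patients with a serious TEAE. The rule also leaves no room for the case-by-case judgment that its own footnote has just asked for.

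The percentage with any serious TEAE is among the first safety figures a reader compares between arms. Protocol V5 is dated June 2021 and enrollment was halted in November 2022, so background infection could make up a large part of it. Protocol section 9 leaves infection screening to local policy, so the number of asymptomatic positives also depends on how often each site tests.

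The SAP offers no way to recover the figure without these infections. The COVID-19 row includes suspected cases that need not have a positive test. It does not show which patients also had another serious event, so it cannot be subtracted from the serious TEAE row. Elsewhere the SAP does isolate COVID-19: in the protocol deviations (12.4), the imputation strategy (12.5.2.2.1) and a supplemental analysis of the primary endpoint (12.5.2.3.4.3).

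**Working it through.** **Plan figures.** The documents state no SAE rate and no COVID-19 rate, so there is no figure to reproduce on this point. The only design figure used is 223 patients per arm (Protocol 13.1). Because the trial stopped before reaching that number, the standard errors below are on the low side.

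**Assumptions (not in the documents).** Risk p of a serious TEAE other than COVID-19: 2% placebo, 4% nabiximols. Risk c of a positive test in the TEAE window: 3% to 15%, the same in both arms and independent of p.

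**Formulas.**
- Rate shown in the table: q = 1 − (1 − p)(1 − c).
- Difference: q1 − q0 = (p1 − p0)(1 − c), so it shrinks only by the factor (1 − c).
- Standard error of the difference: √[q0(1 − q0)/223 + q1(1 − q1)/223].
- Share of placebo patients counted only because of COVID-19: 1 − p0/q0.

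Example at c = 5%: q0 = 1 − 0.98 × 0.95 = 0.069 and q1 = 1 − 0.96 × 0.95 = 0.088. The ratio is 0.088/0.069 = 1.28 and the difference is 1.90 points.

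| c | Placebo | Nabiximols | Ratio | Difference (points) | SE (points) | Placebo share due only to COVID-19 |
|---|---|---|---|---|---|---|
| 0% | 2.00% | 4.00% | 2.00 | 2.00 | 1.61 | 0% |
| 3% | 4.94% | 6.88% | 1.39 | 1.94 | 2.23 | 60% |
| 5% | 6.90% | 8.80% | 1.28 | 1.90 | 2.55 | 71% |
| 10% | 11.80% | 13.60% | 1.15 | 1.80 | 3.15 | 83% |
| 15% | 16.70% | 18.40% | 1.10 | 1.70 | 3.60 | 88% |

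**Other base rates.** With 3% v 6%, c = 3% gives 1 − 0.97 × 0.97 = 5.91% v 1 − 0.94 × 0.97 = 8.82%, a ratio of 1.49. At c = 15% it is 17.55% v 20.10%, a ratio of 1.15.

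**If infections are not balanced.** With 2% v 4% again, suppose 5% of placebo and 3% of nabiximols patients test positive. The table shows 6.90% v 6.88%, a ratio of 1.00. Reverse the infection rates and it shows 4.94% v 8.80%, a ratio of 1.78. Chance imbalance can move the aggregate either way.

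The dilution is an upper bound. Some infections would meet another criterion and belong in the count on any reading.

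**The case against.** A reader might infer that Protocol 12.2 flatly contradicts itself. The documents do not establish that. The COVID-19 sentence sits in the footnote to the sixth criterion, so it can be read as deeming every positive test medically significant, and on that reading it meets the restrictive rule. The text does not say so, and an automatic rule fits poorly with the judgment called for just before it. The wording is unclear rather than plainly contradictory. For the same reason, counting only events that meet one of the six criteria is not a safe repair. It would either change nothing or make the analysis override recorded seriousness.

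A reader might also infer that a real safety signal would be hidden. That goes too far. COVID-19 terms have their own lines in the SOC/PT table, and other PT rows, where a specific signal would appear, are unaffected. The death rows, and the overall row for serious events related to IMP, are largely unaffected. Listings show preferred term, severity, outcome and seriousness. Serious TEAEs are presented descriptively with no test, and 2% v 4% of 223 is only about 4 v 9 patients, so clean data would not settle the comparison either. Positive tests before the first dose are not TEAEs, and no scheduled COVID-19 testing is required.

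These points confine the problem to the aggregate rows. They do not supply the missing figure: the number of patients per arm with a serious TEAE other than COVID-19.

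**Conclusion.** The point holds in a limited form and is minor. Followed as written, the plan lets on-treatment infections of any severity into the rows for any serious TEAE and for the infection SOC, with no companion figure that leaves them out. Under the assumed 2% v 4%, with 3% to 15% positive in both arms, the placebo rate rises from 2% to between 4.9% and 16.7%, the ratio falls from 2.0 to between 1.39 and 1.10, and the standard error grows from 1.6 to between 2.2 and 3.6 points. The absolute difference falls only from 2.0 to between 1.94 and 1.70 points. All of these rates are assumptions, and so are balance between arms and independence from other serious events. The existence of the gap does not depend on them. No efficacy result, alpha or power figure is affected.

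**What to change.** 1. In Protocol 12.2, or in a note to the SAP, state whether a positive test is deemed medically significant or only needs expedited recording, and reconcile this with the restrictive rule. The recording instruction itself can stay.
2. Keep the full serious TEAE row and tables. In SAP 12.8.1.2 and 12.8.2.2, or in the addendum, add a by-arm row and an SOC/PT summary of serious TEAEs excluding COVID-19 terms identified under SAP 10.23.2.
3. If the eCRF captures the seriousness criterion for each event, which the documents do not show, exclude only COVID-19 events that meet no other criterion.
4. Review the matched serious events before unblinding, because a text search picks up any term containing the name and misses terms worded differently.

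The cost is one row, one table and a footnote explaining why the two counts differ. The simpler version in step 2 also drops COVID-19 cases that were truly serious, but these stay visible in the full table and the listing. If the summary can only be added after unblinding, label it post hoc.

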# 12.3 Reporting Procedures for Serious Adverse Events

All SAEs occurring during the trial must be reported to GW with any other supporting information and recorded in the AE section of the eCRF. Any ongoing SAEs should be followed up until resolution wherever possible. For all deaths, the working diagnosis or cause of death as stated on a death certificate, available autopsy reports, and relevant medical reports should be sent to GW promptly.

All SAEs must be reported in the eCRF within 24 hours of discovery or notification of the event (see APPENDIX 2). The GW Pharmacovigilance Department (PVD) will be automatically notified that an SAE has been recorded. Any additional information required for a case (follow-up of corrections to the original case) will be requested by GW PVD through eCRF queries.

The investigator is not obliged to actively monitor for any new SAEs that occurred after the last formal Safety Follow-up Visit (Visit 7). However, if the investigator becomes aware of any deaths or a new IMP-related SAE occurring within 28 days of the final dose of IMP, these should be reported to the GW PVD.

Any other problem discovered after Visit 7 that is deemed to be an unexpected safety issue and is likely to have an impact on patients who have taken part in the trial must be treated as an SAE and reported to the GW PVD. Such post-trial SAEs do not need to be recorded on the patient's eCRF if editing rights to the eCRF have been removed due to final trial data lock. The GW PVD may request safety follow-up information after the final trial visit in order to investigate a potential safety issue.

Contact details for the GW PVD are provided at the front of the site files for all trial sites and on the GW SAE report form.

